#### Sensitivity Analyses

The primary analysis will be repeated using the PP population.

The primary analysis will be repeated using a two-sided test at the 5% level.

The primary analysis will be repeated using the last observation carried forward (LOCF) method to substitute a missing PaO2/FiO2 ratio for patients extubated within 24 hours after ICU submission. For patients who died within 24 hours of ICU admission a ratio of 0 will be used at the 24 hour time point. Data for patients with a ratio missing for any other reason will not be substituted.

The primary analysis will be performed including the type of transplant (single or double) as a fixed effect covariate whose importance will be assessed at the 5% level. The interaction term for type of transplant and treatment will also be fitted but if this is not significant at the 10% level it will be excluded from the final model. The randomization has not been stratified by the type of transplant and therefore this analysis will only be performed if there are sufficient data within each treatment, center and type of transplant combination.

In summary, the following presentations of PaO2/FiO2 ratio at time 0 and 24 hours will be produced:

Repeated Measurements Analysis using a one-sided test for the ITT population with missing data excluded.

Repeated Measurements Analysis using a one-sided test for the PP population with missing data excluded.

Repeated Measurements Analysis using a two-sided test for the ITT population with missing data excluded.

Repeated Measurements Analysis using a one-sided test for the ITT population with substitution of missing data.

Repeated Measurements Analysis using a one-sided test for the ITT population including type of transplant but with missing data excluded.

Repeated Measurements Analysis using a one-sided test for the PP population including type of transplant but with missing data excluded.

Additional exploratory analyses may be performed to further investigate the robustness of the primary efficacy data.

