9.4.2. Primary efficacy analysis

The PaO₂/FiO₂ ratio will be analyzed separately, at the two time points: 0 hours (ICU admission) and 24 hours after ICU admission. Analysis of variance will be used, including terms for treatment and center. The importance of the treatment by center interaction will be investigated but if this is not significant at the 10% level, this term will be excluded from the final model. If a center by treatment interaction is detected, alternative methods of presentation will be explored. Treatment effect will be primarily compared using a one-sided 0.05 level test and then re-tested for consistency with a two-sided 0.05 level test. Type of transplant (single or bilateral) will then be included in the model of the analysis to explore any possible, even unanticipated, differences due to the specific procedure.

Primarily the data will be analyzed excluding missing data. As confirmatory analysis, the ANOVAs will be performed substituting any missing values by the last observation carried forward (LOCF) method, in patients extubated before 24 hours. If the data are missing due to

patient death, the PaO₂/FiO₂ ratio will be given a zero value. If the data are missing due to lack of recording while on mechanical ventilation, these data will not be substituted.

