### 6.1 Intention-to-treat (ITT)

The ITT population will consist of all randomized patients who received any study medication and a lung transplant. Patients will be analyzed according to the treatment randomized regardless of which treatment was actually received.

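### The SAP's zero-for-death rule is narrower than the protocol's: a transplanted patient who dies before ICU admission gets no zero at either time and leaves the substitution analysis

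*SAP*

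**What the plan says.** Protocol 9.4.2 has the ratio "analyzed separately, at the two time points: 0 hours (ICU admission) and 24 hours after ICU admission". The main analysis leaves missing values out. A confirmatory run of the ANOVAs then substitutes in two ways: LOCF for patients extubated before 24 h, and a rule for death under which, if data are missing because of "patient death, the PaO₂/FiO₂ ratio will be given a zero value". The death rule names no time point and no place of death. Only one category is expressly left alone: "If the data are missing due to lack of recording while on mechanical ventilation, these data will not be substituted".

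SAP 9.5.1 (Sensitivity Analyses) keeps LOCF for early extubation and then states: "For patients who died within 24 hours of ICU admission a ratio of 0 will be used at the 24 hour time point". It closes with: "Data for patients with a ratio missing for any other reason will not be substituted".

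On who is analysed, SAP 6.1 reads: "The ITT population will consist of all randomized patients who received any study medication and a lung transplant". Protocol 9.3 has the same two conditions, study drug and transplant. Neither document requires arrival in the ICU. SAP section 5 fixes time 0 as the date and time of ICU admission. SAP 1.2 reports no changes from the protocol.

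**The concern.** The SAP adds two limits that the protocol rule does not have: the 24 h time point only, and death within 24 hours of ICU admission only. It neither declares nor explains them.

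The patients affected are those who die earliest. The infusion starts about two hours before reperfusion (Protocol 6.2), so a death in the operating room after implantation follows exposure to study drug. Of the six presentations of the 0 h and 24 h ratio listed in SAP 9.5.1, only the one reported as Table 2.1.4 substitutes for missing values, and the 48 h and 72 h analyses (SAP 9.5.2.1) also exclude them. Table 2.1.4 is therefore the only place where a death can count against an arm on PaO2/FiO2. If patients who die before the ICU are absent from it, that analysis compares only those who survived to ICU admission, and the arm with more such deaths looks better than it would under the protocol rule.

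**Working it through.** **Step 1. The two rules, case by case, in the substitution analysis (ITT).**

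| Patient | Protocol 9.4.2: 0 h / 24 h | SAP 9.5.1, literal: 0 h / 24 h |
|---|---|---|
| Dies after transplant, before ICU admission | 0 / 0 | missing / missing |
| Dies in the ICU, within 24 h, before the time-0 gas | 0 / 0 | missing / 0 |
| Time-0 gas taken, then dies before 24 h | measured / 0 | measured / 0 |
| Ventilated at the time point, gas not recorded | not substituted | not substituted |
| Extubated before 24 h, 24 h ratio missing | measured / LOCF | measured / LOCF |

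The rules differ in the first two rows only. In the first row the patient has no ICU admission time, so the SAP condition cannot be met. With no value at either time the patient contributes nothing to the repeated measurements model. In the second row only the 0 h zero is lost.

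**Step 2. The plan's own figures.** Inputs from Protocol 9.1: 50 per arm, SD 137, one-sided 0.05, two-group t-test. The standard error of the difference is 137 × √(2/50) = 27.4 mmHg, so the noncentrality is 70/27.4 = 2.55 or 50/27.4 = 1.82. With 98 df the power is 81.4% and 56.6%, against the stated 81% and 56%. These reproduce. The zero rule plays no part in them.

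**Step 3. Effect of an omitted pre-ICU death on raw means.** If k of 50 patients in an arm with mean m should score zero, the arm mean is m(50 − k)/50. If they are left out, it is m. The shift is km/50. With the historical means in Protocol 9.1 (329 at ICU admission, 315 at 24 h):

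| k (assumed) | Shift at 0 h, mmHg | Shift at 24 h, mmHg | Share of 70 mmHg |
|---|---|---|---|
| 1 | 6.6 | 6.3 | 9% |
| 2 | 13.2 | 12.6 | 18–19% |
| 3 | 19.7 | 18.9 | 27–28% |

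In an arm at the design treated mean of 385 the 24 h figure per patient would be 385/50 = 7.7 mmHg. For scale, one zero at 0 h raises that arm's SD to 143.4 and the standard error of the difference to 28.0, so the shift is 6.6/28.0 = 0.23 of a standard error.

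**Step 4. Effect on the test.** A simulated two-group t-test (40,000 runs, means 315 and 385, SD 137, one-sided 0.05) gave these rejection rates:

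| Assumed pre-ICU deaths | Omitted | Scored zero |
|---|---|---|
| 2 on repertaxin only | 81% | 59% |
| 2 on placebo only | 80% | 90% |
| 2 in each arm | 80% | 74% |

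The direction depends on the arm in which the deaths fall. The SAP's mixed model was not simulated.

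**Step 5. A death in the ICU before the time-0 gas.** The 24 h zero stays in, and the within-patient correlation r pulls the 0 h estimate part of the way down. Assuming equal SDs and separate means at each time, about r × 6.3 mmHg of the 6.6 is recovered. The documents give no r. For an assumed r of 0.3 to 0.7 this is 1.9 to 4.4 mmHg, which leaves roughly 2 to 5 mmHg at 0 h and nothing lost at 24 h.

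**The case against.** The best defence is that the SAP merely puts the protocol's rule into operation. The endpoint is defined by ICU admission (Protocol 4.2.1.1), so a patient who never reaches the ICU has neither time point. Protocol 9.4.2 does not mention death before the ICU, and its zero rule follows directly on an LOCF rule that concerns the 24 h value. This shows a gap in the protocol, but it does not remove the difference. The protocol rule follows an instruction covering the ANOVAs at both times, the 24 h limit is attached only to extubated patients, and the ITT definition keeps the pre-ICU death in the population.

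The second defence is that little depends on it, and most of that stands. One sensitivity output changes. The deaths are reported elsewhere: 30-day mortality by arm, counted from reperfusion (SAP 9.5.2.5), and deaths in the adverse-event summary from the start of infusion (SAP 9.6.2). The DMC also monitors deaths by arm (Protocol 8.5). The millimetre figures are raw-mean illustrations with an assumed number of deaths, and in a balanced trial the shifts largely cancel between arms.

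A reader might also count a patient who dies shortly after 24 h with no gas taken, because Protocol Appendix 6 allows ±2 hours. The documents do not settle that case. The patient was alive at the scheduled time, and if still ventilated the gap can equally be read as a value not recorded, which the protocol leaves unsubstituted.

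**Conclusion.** The point holds, at modest size. The SAP does not carry out the death rule that the protocol states, and it declares no departure. A death after transplant but before ICU admission loses both zeros and leaves Table 2.1.4. A death in the ICU before the time-0 gas loses only the 0 h zero.

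The size rests on an unknown count. Each omitted pre-ICU death in one arm moves that arm's raw mean by about 6.6 mmHg at 0 h and 6.3 mmHg at 24 h, assuming 50 per arm and the historical means. The effect of a pre-gas ICU death is smaller. The number affected may be zero.

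Two stronger inferences are not supported. The primary result is not biased by this wording, because both documents exclude missing values there. Nor are the deaths hidden from the report; they are absent only from the PaO2/FiO2 comparison. Whether zero is the right score for a death is a separate question.

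**What to change.** Before database lock, replace the SAP sentence on deaths with wording such as: *If the ratio at 0 h or 24 h is missing because the patient died before that assessment, including death after transplantation but before ICU admission, a ratio of 0 will be used at each such time point.* Limit the closing bar on substitution to values missing for reasons other than death. If the sponsor intends the narrower rule, list it in SAP 1.2 with the reason.

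The cost is one sentence. Reperfusion times (Protocol 7.3) and a death report (SAP Listing 4.15) are already planned, and the primary analysis does not change. Under SAP 1.1 and 8.2 the plan is finalised before lock and unblinding follows lock, so the choice can be made blind. Made after unblinding, it would be open to influence from the results.

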## 9.5.2 Secondary Variables

### 9.5.2.1 PaO2/FiO2 ratio at 48 hours and 72 hours after ICU admission

These data will be analyzed as described for the primary analysis using a one-sided test at the 5% level and with missing data excluded. A further analysis including type of transplant again using a one-sided test at the 5% level and with missing data excluded will also be performed provided there are sufficient data recorded. Both these analyses will be performed on the ITT and PP analysis populations.

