9.4. STATISTICAL METHODOLOGY

Appropriate descriptive statistics will be produced, according to the variable. For continuous data the mean, standard deviation, median and range (minimum and maximum) will be presented. For categorical data, frequencies and percentages will be presented. If appropriate, confidence intervals around the mean or the proportions will be presented.

All patient data collected on the CRF will be listed by patient, treatment group and center.

The data for the double-blind phase of the study (up to 30 days post-treatment) will be presented in the clinical study report. Data collected during the open phase of the study (from 1 month up to 12 months) will be presented in an addendum to the clinical study report.

Unless otherwise specified, the significance level used for statistical testing will be 5% and two-sided tests will be used.

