9.4.3. Secondary efficacy analysis

The PaO₂/FiO₂ ratio will be analyzed, as described for the primary efficacy endpoint, at 48 hours and 72 hours after ICU admission. Analysis of variance will be used, including terms for treatment and center. The importance of the treatment by center interaction will be investigated but if this is not significant at the 10% level, this term will be excluded from the final model. If a center by treatment interaction is detected, alternative methods of presentation will be explored. Type of transplant (single or bilateral) will then be included in the model of the analysis to explore any possible, even unanticipated, differences due to the specific procedure.

Analysis of PGD score will be performed separately at the four time points (0, 24, 48, 72 hours) to test for differences between treatments. Two analyses will be performed at each time-point, using Cochran-Mantel Haenszel statistics, with the first analysis using type of transplant as a stratification factor, and the second using center as a stratification factor.

The time to freedom from mechanical ventilation and the duration of ICU stay will be presented using Kaplan-Meier plots, and will be analyzed using the Median test, to test for differences between treatments. Time to freedom from mechanical ventilation and the duration of ICU stay will also be presented by type of transplant, and the Median test will be performed on each type of transplant, if there are sufficient patient numbers in both categories.

All other secondary endpoints will be presented using appropriate descriptive statistics, and no formal statistical testing will be performed.

ICU mortality and the number of patients who die within the first 30 days post transplant will be tabulated. FEV₁ and FVC at 1 month post-transplant will be presented by type of transplant.

FEV₁ and FVC, BOS score, cumulative acute rejection episodes and patient survival at 6 and 12 months post-transplant will be presented in an addendum to the clinical study report, using descriptive statistics. BOS score, cumulative acute rejection episodes and patient survival will also be presented by type of transplant.

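### The SAP plans no two-sided 5% test of PaO2/FiO2 at 48 h and 72 h, although the protocol calls for one at each time point, and it does not declare the omission

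*SAP*

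**What the plan says.** **Protocol.** Section 9.4 sets the general rule: "Unless otherwise specified, the significance level used for statistical testing will be 5% and two-sided tests will be used". For the primary endpoint at 0 h and 24 h, section 9.4.2 specifies otherwise: "Treatment effect will be primarily compared using a one-sided 0.05 level test and then re-tested for consistency with a two-sided 0.05 level test". For the later time points, section 9.4.3 has the ratio analysed "as described for the primary efficacy endpoint, at 48 hours and 72 hours after ICU admission". It then restates the ANOVA, the treatment-by-center interaction rule and the transplant-type model, and is silent on sidedness.

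**SAP.** Section 9.5.2.1 says of 48 h and 72 h: "These data will be analyzed as described for the primary analysis using a one-sided test at the 5% level and with missing data excluded". The transplant-type model is handled the same way: "A further analysis including type of transplant again using a one-sided test at the 5% level and with missing data excluded". Tables 2.2.1 to 2.2.4, the only tables for these time points, are all titled as one-sided. A two-sided repeat exists ("The primary analysis will be repeated using a two-sided test at the 5% level"), but it is a sensitivity analysis of the primary variable, and its Table 2.1.3 covers 0 h and 24 h only. SAP 1.2 lists no changes from the protocol.

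**The concern.** The protocol and the SAP do not apply the same significance test to the 48 h and 72 h ratios. The results affected are those favouring repertaxin with a one-sided p-value between 0.025 and 0.05: the SAP calls them significant, and the protocol's two-sided test does not. A reader who relies on SAP 1.2 would assume that the two documents agree.

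The case for a one-sided test in the sample size sections (Protocol 9.1, SAP 3.2) concerns the primary endpoint. It does not extend to 48 h and 72 h, where the ratio is measured only in patients not yet extubated (Protocol 4.2.1.2).

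**Working it through.** **1. Reproduce the plan's own figure.** Inputs from Protocol 9.1: 50 per arm, SD 137 mmHg, two-group t-test, one-sided 0.05. The standard error is 137 × √(2/50) = 27.4 mmHg, with 98 degrees of freedom. Power comes from the noncentral t distribution with noncentrality difference/27.4.

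| Difference | Stated power | One-sided 5% | Two-sided 5% |
|---|---|---|---|
| 70 mmHg | 81% | 81.4% | 71.6% |
| 50 mmHg | 56% | 56.7% | 43.9% |

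The stated figures are reproduced only by the one-sided test, so one-sided testing is a real design choice for the primary comparison. Neither document makes a power statement for 48 h or 72 h.

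**2. What the protocol requires at 48 h and 72 h.** There are two fair readings of Protocol 9.4.3.

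- *The 9.4 rule governs.* Section 9.4.3 repeats much of 9.4.2 but leaves out the sentence on sidedness, so the two-sided default applies. The two-sided 5% test is then the only test.
- *The 9.4.2 method is carried over.* The cross-reference to the primary endpoint brings the sidedness sentence with it. That sentence has two parts: a leading one-sided 0.05 test and a two-sided 0.05 re-test. The two-sided 5% test is then the consistency check.

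A two-sided 5% test is due under both readings.

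**3. Size if the 9.4 rule governs.** The error rate in the favourable tail is 0.05/2 = 0.025 under the protocol and 0.05 under the SAP. The critical z is 1.960 against 1.645, and 1 − 1.645/1.960 = 16%.

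The smallest significant difference is t × SD × √(2/n). The documents do not say how many patients will have a value at 48 h or 72 h, and they give no SD for them. I assume 10 to 50 per arm and borrow the SD of 137:

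| n per arm | One-sided 5% (mmHg) | Two-sided 5% (mmHg) | Reduction |
|---|---|---|---|
| 10 | 106.2 | 128.7 | 17.5% |
| 30 | 59.1 | 70.8 | 16.5% |
| 50 | 45.5 | 54.4 | 16.3% |

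The percentage reduction is a ratio of critical t values, so it does not depend on the SD.

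The chance of a false favourable result at one or both time points, if the two were independent, is 1 − 0.95² = 9.75% under the SAP and 1 − 0.975² = 4.9% under the protocol. With an assumed correlation of 0.5 it is 8.8% against 4.5%; for correlations from 0.3 to 0.7 it runs from 9.3% to 8.0% against 4.8% to 4.2%.

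**4. Size if 9.4.2 is carried over.** The leading test is one-sided 0.05 in both documents, so its threshold does not move. What is lost is the re-test, and with it any sign that a result with one-sided p between 0.025 and 0.05 fails the two-sided check.

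**5. Whether other planned output fills the gap.** The shell for Tables 2.1.x and 2.2.x prints a Type III F test for treatment, which is non-directional. It is one test of treatment over the two time points, not a test at each. The interval in SAP 9.5.1 is built with α = 0.10 and its lower limit is replaced by −∞, so, if carried over to 48 h and 72 h, it is not a two-sided 95% interval either.

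**The case against.** The strongest reply is that Protocol 9.4.3 refers back to the primary endpoint, and that this can fairly count as specifying otherwise for the purposes of 9.4. The SAP then keeps the protocol's leading test and omits only a consistency check. Nor is the one-sided test concealed: it is stated in SAP 9.5.2.1 and in every 48 h and 72 h table title. The shell gives the difference, its standard error and a p-value, so a two-sided p-value can be derived. The protocol labels these endpoints exploratory, SAP 9.5.1 says the study is not pivotal, and no decision rule depends on them.

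Most of this stands, and it limits the severity. It does not supply the re-test, which belongs to the same sentence of 9.4.2, and it does not make SAP 1.2 accurate. A p-value that a reader can work out is not a planned analysis.

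A reader might also infer that a result unfavourable to repertaxin could never be detected. The documents do not support that. The one-sided p-value would not flag it, but the interval described in SAP 9.5.1 keeps its upper limit, and an upper limit below zero for repertaxin minus placebo would show harm. The F test is also sensitive to either direction.

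**Conclusion.** The omission is real and undeclared: the protocol calls for a two-sided 5% test at each of 48 h and 72 h under either reading, and the SAP plans none. Its consequence depends on which reading governs. Under the 9.4 rule, the favourable-tail error rate per time point is 5% instead of 2.5%. Under the carried-over method, only the re-test is missing.

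A reader might infer that the bar for success has been halved. That goes too far. The error rate doubles only if the 9.4 rule governs, and even then the difference needed for significance falls by about 16-18%.

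The mmHg figures rest on the assumed 10 to 50 patients per arm and the borrowed SD of 137, and the either-time-point figures rest on the assumed correlation. The textual finding rests on neither. One caveat is that the SAP was written against the protocol dated 30 August 2005 (SAP 1.1), and the date of the protocol at hand is not visible. The severity is minor because the endpoints are exploratory.

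**What to change.** 1. In SAP 9.5.2.1 and Tables 2.2.1 to 2.2.4, add for each of 48 h and 72 h the two-sided 5% p-value and a full two-sided 95% confidence interval for repertaxin minus placebo.
2. State in SAP 9.5.2.1 which sidedness leads, consistent with Protocol 9.4 and 9.4.3. The protocol text allows either order, so this should be settled explicitly.
3. Record any remaining departure in SAP 1.2, with the reason.

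The cost is a few lines of SAP text and one output option, with no new data. SAP 1.1 has the plan finalised before database lock, so the change can be made before unblinding. The downside is that some favourable 48 h or 72 h results will not be significant on the two-sided test.

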### 9.5.2.2 PGD score

Analysis of PGD score will be performed separately at time 0 and at 24, 48 and 72 hours after ICU admission. Two analyses, using Cochran-Mantel-Haenszel statistics from PROC FREQ within SAS, will be performed at each time point. The first will use type of transplant (single or double) as a stratification factor and will use the following SAS code:

```
Proc freq data=data1 (where=(time=x)) noprint ;  
  table tran_typ*PGD*treat/cmh out=ct_typ ;  
  output out=cmh type cmh ;  
run ;
```

As the randomization did not include type of transplant it is possible that there will be insufficient data within each of the cells to perform the analysis. This will be assessed after the Month 1 database lock.

The second analysis will use center as a stratification factor.

Both analyses will be performed for both the ITT and PP populations. For each analysis, the number and percentage of patients within each table cell will be presented, together with the second of the three p-values provided by PROC FREQ (labeled as Row Mean Scores Differ), and the corresponding Mantel-Haenszel odds ratio and the associated 95% confidence interval.

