2.4. DISEASE REVIEW AND STUDY RATIONALE

Lung transplantation has become a standard therapy for patients with end-stage lung disease. Within last decades, donor management, organ preservation, immunosuppressive regimens and control of infectious complications have been substantially improved. In addition, the operative techniques of transplantation procedures have been developed to an international standard of high quality [Lau & Patterson, 2003].

However, despite these refinements, significant reperfusion injury occurs in up to 10-20% of lung transplant recipients as the consequence of unavoidable processes of procurement, preservation and restoring blood flow. This clinical condition, recently termed primary graft dysfunction (PGD), remains an important problem after lung transplantation [Christie, 1998; King, 2000], and still represents the single biggest cause of early morbidity and mortality for lung recipients [Fischer, 2001; Thabut, 2002]. In addition, there is some evidence to suggest a relationship between reperfusion injury, acute rejection, and the subsequent development of chronic graft dysfunction [Waddell, 1996; Fiser, 2002].

Prediction of PGD is made difficult by the complexity of the interactions between the donor lung and the recipient [Sommers, 1996; McRae, 2000].

In post-ischemia reperfusion, restoration of the blood supply (reperfusion) after prolonged tissue ischemia is associated with an inflammatory reaction characterized by massive polymorphonuclear neutrophil infiltration into the reperfused tissue [de Perrot 2003]. The infiltrating inflammatory cells can perpetuate the initial inflammatory reaction and induce further injuries.

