4. OBJECTIVES AND ENDPOINTS

4.1. STUDY OBJECTIVES

The objective of this clinical trial is to evaluate whether CXCL8 inhibition with repertaxin leads to reduced severity of PGD, as the result of improved functional and clinical outcomes in lung transplantation patients. The safety of repertaxin in the specific clinical setting will be also evaluated.

The ability of repertaxin to reduce target cells (PMN) infiltration into the graft will be evaluated to confirm its mechanism of action. Plasma levels of repertaxin and its major metabolite will be measured at steady state conditions to provide population pharmacokinetic profile in this specific clinical setting.

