14. APPENDICES

14.1. APPENDIX 1 - METHODOLOGICAL DETAILS

14.1.1. PGD score - ISHLT system for grading of severity of primary graft dysfunction [*Christie et al, 2004*]

Grade 0	$\text{PaO}_2/\text{FiO}_2 \geq 300$ mmHg; no radiographic infiltrates
Grade 1	$\text{PaO}_2/\text{FiO}_2 \geq 300$ mmHg + radiographic infiltrates consistent with pulmonary oedema
Grade 2	$200 \text{ mmHg} \leq \text{PaO}_2/\text{FiO}_2 < 300$ mmHg + radiographic infiltrates consistent with pulmonary oedema
Grade 3	$\text{PaO}_2/\text{FiO}_2 < 200$ mmHg + radiographic infiltrates consistent with pulmonary oedema

Any patient with no infiltrate on chest X-rays is automatically grade 0, regardless of $\text{PaO}_2/\text{FiO}_2$ value. If the patient is on nasal cannula for oxygen or $\text{FiO}_2 < 0.3$, the patient is graded as 0 or 1, based on chest X-rays. Any patient on extra corporeal membrane oxygenation is automatically grade 3. Any subject mechanically ventilated with FiO_2 greater than 0.5 or requiring nitric oxide beyond 48 hours from the time of transplant should be considered grade 3.

If multiple blood gas values are available, the worst $\text{PaO}_2/\text{FiO}_2$ ratio will be used for the purpose of this grading scheme.

PGD score will be evaluated at the following time points:

- Time-0 (T0): defined as within 6 hours of final lung reperfusion. The first blood gas in ICU is ideal for this. Ideally, measurement should be done on $\text{FiO}_2 1.0$ and PEEP =5 while still on mechanical ventilation.
- T24, T48, T72: Later times being measured at potentially multiple time points after 24 hours, up to 72 hours. Time will be measured following $T0 \pm 6$ hours.

Chest X-rays will be graded by an Investigator, and then validated by a (blinded) transplant radiologist.

In patients with clinical diagnosis of PGD additional time points will be considered up to the clinical recovery of the condition as per available data according to center standard of care.

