## 2 STUDY OBJECTIVES

To evaluate whether CXCL8 inhibition with repertaxin leads to reduced severity of primary graft dysfunction (PGD), as the result of improved functional and clinical outcomes in lung transplantation patients.

The safety of repertaxin in the specific clinical setting will also be evaluated.

The ability of repertaxin to reduce target cells (PMN) infiltration into the graft will be evaluated to confirm its mechanism of action. Plasma levels of repertaxin and its major metabolite will be measured at steady state conditions to provide population pharmacokinetic (PK) profile in this clinical setting.

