#### PGD Score

This is graded as an integer between 0 and 3 according to the following definitions:

Grade 0	no radiographic infiltrates
Grade 1	$\text{PaO}_2/\text{FiO}_2 \geq 300$ mmHg + radiographic infiltrates consistent with pulmonary oedema
Grade 2	$200 \text{ mmHg} \leq \text{PaO}_2/\text{FiO}_2 < 300$ mmHg + radiographic infiltrates consistent with pulmonary oedema
Grade 3	$\text{PaO}_2/\text{FiO}_2 < 200$ mmHg + radiographic infiltrates consistent with pulmonary oedema

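### Patients who die before a PGD assessment have no grade and drop out of the later PGD comparisons, which favours the arm with more early deaths if deaths differ by arm

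*SAP*

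**What the plan says.** The objective in Protocol 4.1 is to "evaluate whether CXCL8 inhibition with repertaxin leads to reduced severity of PGD". The PGD score is listed among the secondary, exploratory endpoints in Protocol 4.2.1.2. It is one of the few secondary endpoints that Protocol 9.4.3 tests formally.

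SAP section 5 says of the score: "This is graded as an integer between 0 and 3 according to the following definitions". Grade 0 is an X-ray without infiltrates. Grades 1 to 3 combine infiltrates with bands of PaO2/FiO2. Protocol Appendix 1 (14.1.1) adds special rules: "Any patient on extra corporeal membrane oxygenation is automatically grade 3", and ventilation with FiO2 above 0.5, or a need for nitric oxide, beyond 48 hours also counts as grade 3. Death appears in neither place.

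SAP 9.5.2.2 sets the timing: "Analysis of PGD score will be performed separately at time 0 and at 24, 48 and 72 hours after ICU admission". It plans Cochran-Mantel-Haenszel (CMH) analyses at each of these time points and gives no rule for deaths or missing grades. SAP 9.1 bases percentages on non-missing responses, the PROC FREQ code has no option to keep missing values, and the shell for Table 2.3.x has rows for grades 0 to 3 only.

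The SAP does deal with death elsewhere. For the PaO2/FiO2 sensitivity analysis in 9.5.1: "For patients who died within 24 hours of ICU admission a ratio of 0 will be used at the 24 hour time point". In 9.5.2.3, a death during ventilation is censored, and 9.5.2.4 analyses ICU stay in the same way.

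**The concern.** Protocol 2.4 says that PGD "still represents the single biggest cause of early morbidity and mortality for lung recipients". A grade that is missing because of death may therefore be missing because the graft failed. Dropping these patients takes some of the worst outcomes out of the score that grades severity. The arm with more early deaths from graft failure then looks better among its survivors.

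The existing death rules do not close the gap. The ratio of 0 is confined to the 24-hour sensitivity analysis of the primary variable, and a ratio without an X-ray yields no grade above 0. Censoring applies only to the time-to-event analyses.

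**Working it through.** **The plan's own figures.** The documents give no power or sample size for the PGD score. Their power figures are for PaO2/FiO2 (Protocol 9.1, SAP 3.2): 50 per arm, SD 137 mmHg, one-sided 0.05. The standard error is 137 × √(2/50) = 27.4, so the noncentrality is 70/27.4 = 2.55 and 50/27.4 = 1.82. The noncentral t with 98 df gives power of 81.4% and 56.6%, against the stated 81% and 56%. These figures reproduce. Only the arm size of 50 carries over to the PGD score.

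**Who leaves, and when.** Each time point is analysed separately. A patient who dies at 40 hours counts at 0 and 24 hours and is absent at 48 and 72. A patient in the ITT population (drug and transplant received) who dies before reaching the ICU is absent at all four.

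**Grade 3 share at 72 hours, 50 per arm.** All counts are assumed. With g surviving grade 3 patients and d deaths, the share is g/(50 − d) with deaths dropped and (g + d)/50 with deaths counted.

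- Deaths 3 v 1, surviving grade 3 5 v 8 (repertaxin v placebo). Dropped: 5/47 = 10.6% v 8/49 = 16.3%, a difference of 5.7 points. Counted: 8/50 = 16.0% v 9/50 = 18.0%, a difference of 2.0 points.
- Deaths 3 v 0, surviving grade 3 6 v 8. Dropped: 6/47 = 12.8% v 8/50 = 16.0%. Counted: 9/50 = 18.0% v 8/50 = 16.0%. The direction changes.
- Deaths 3 v 3, with 10 grade 3 or fatal cases in each arm. Dropped: 7/47 = 14.9% in both. Counted: 10/50 = 20.0% in both. There is no bias between arms, but severity is understated.

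**Effect on the test.** This was simulated with 8,000 trials per scenario, 50 per arm, and an unstratified one-df mean-score test at two-sided 5%. Grades 0 to 3 were assumed at 40/25/15/20% in both arms, with all deaths drawn from grade 3. The table gives the rate of significant results favouring repertaxin when the true grades are equal (nominal 2.5%).

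| Share of grade 3 patients who die, repertaxin v placebo | Deaths dropped | Deaths as grade 3 |
|---|---|---|
| 50% v 0% | 14.6% | 2.6% |
| 40% v 10% | 8.4% | 2.8% |
| 25% v 25% | 2.5% | 2.7% |
| 10% v 10% | 2.4% | 2.4% |

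With a real benefit (assumed 52/26/12/10% v 40/25/15/20%) and equal lethality of 0, 10, 25 or 50% in grade 3, power with deaths dropped is 36, 34, 30 and 25%. With deaths counted as grade 3 it stays at 35 to 36%.

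**How the test is coded.** SAP 9.5.2.2 reports "the second of the three p-values provided by PROC FREQ (labeled as Row Mean Scores Differ"). The code is `tran_typ*PGD*treat`, so PGD forms the rows and treatment the columns. That statistic then has 3 df and does not use the order of the grades. Folding deaths into grade 3 works with this layout. A fifth level for death would give 4 df and would not be ranked as worst.

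**The case against.** The strongest case on the other side has four parts.

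- **Deaths are not hidden.** SAP 9.5.2.5 tabulates ICU and 30-day mortality by arm for the ITT population, the listings cover vital status and death reports, and the Data Monitoring Committee (DMC) follows deaths in both arms. This stands. However, the mortality table is descriptive and does not alter the PGD p-value.
- **Some deaths may already carry a grade.** Protocol Appendix 6 allows X-rays within 4 hours of the first two time points and 8 hours of the last two, and Appendix 1 uses the worst available gas. A patient who dies close to a time point may have an in-window grade 3. This stands and limits the gap.
- **The illustrations are within noise.** Fisher's exact p is 0.55 with deaths dropped and 1.0 with deaths counted in the 3 v 1 case, and 0.78 and 1.0 in the 3 v 0 case. No conclusion would change. This also stands: the counts show direction, not a likely result.
- **Scoring death as grade 3 is single-value imputation.** It would count deaths from other causes, while Protocol 7.5.2 excludes secondary causes from clinically diagnosed PGD. This is a real cost and should be stated in the SAP.

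A reader might go further and infer that fatal graft failures vanish from the efficacy comparison altogether. They do not: each patient leaves only the time points after death. A reader might also infer that the plan is tilted towards repertaxin. The documents do not support this either, because the direction depends on which arm has more early deaths, and they give no rate.

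**Conclusion.** The gap is real and should be closed. As written, the plan compares PGD grades among patients alive and graded at each time point, without saying so. If early deaths from graft failure differ by arm, that comparison favours the arm with more of them.

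The size cannot be fixed from the documents. The 5.7 v 2.0 points and the 8.4 to 14.6% false-positive rates rest on assumed counts and grade distributions, and the latter need 40 to 50% of repertaxin grade 3 patients to die against 0 to 10% on placebo. With few deaths the distortion is small. With equal lethality type I error holds, and the cost is some power if the drug works.

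The point concerns a secondary, exploratory endpoint in a study that the SAP itself does not regard as pivotal. Calling the score the most direct measure of the objective would be a judgement: the primary endpoint is PaO2/FiO2, and the objective also refers to functional and clinical outcomes. The point does not touch the primary analysis.

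**What to change.** Before database lock, and so before unblinding, add to SAP 9.5.2.2 that a patient who dies at or before a PGD time point without an in-window grade is counted as grade 3 at that and all later time points. Make this the main PGD analysis, or at least a stated sensitivity analysis parallel to the ratio of 0 in 9.5.1. Add a row to Table 2.3.x with the number of deaths by arm at each time point.

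If a separate level for death above grade 3 is preferred, transpose the table to `tran_typ*treat*PGD`, and likewise in the analysis stratified by center, so that the reported statistic uses the order of the grades.

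State the downside: deaths from causes other than PGD are scored as worst PGD, so the endpoint becomes PGD severity or death.

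The cost is one sentence and one table row, plus a change of table order if the separate level is used. Vital status and death dates are already collected, so no new data are needed.
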